6.2.1 Justification of Dose Selection and Efficacy Analysis

In the adult controlled clinical trials for the LVO and EBD indication, the duration of the useful imaging time for LV chamber opacification was 2.5 to 4.5 minutes for a dose of 0.5 to 3.0 mL [OPTISON PI].

McMahon et al conducted rest non-contrast and CE-ECHO in 20 children (9 to 18 years) with limited transthoracic echo windows [McMahon et al. 2005]. OPTISON was administered at a dose of 0.3 mL per injection for children <20 kg and 0.5 mL per injection for those ≥ 20 kg. The EBD was significantly improved in all patients with CE-ECHO and LVEF was measurable in all 20 patients using contrast echo versus only 11 with non-contrast echocardiography. Zilberman et al performed contrast stress echocardiography with OPTISON administration in 22 children (8 months to 19 years; mean age 9.3 ± 3.9 years) [Zilberman et al. 2003]. A dose of 0.1 mL was given for patients ≤ 25 kg, and 0.2 mL for patients > 25 kg. These doses provided adequate opacification of the LV cavity for up to 60 seconds.

Similar to the two publications, OPTISON dose in this study will be administered based on body weight. According to the Centers for Disease Control and Prevention Pediatric Growth Charts [CDC Growth Charts], children > 9 years of age usually weigh > 28 kg and children > 12 years of age usually weigh > 40 kg for both boys and girls in the United States, but weight varies greatly for a specific age. Two dose levels will be tested in each weight cohort: 0.1 or 0.2 mL per injection to children weighing ≥ 20 to ≤ 28 kg, 0.2 or 0.3 mL per injection to those who weigh > 28 to ≤ 40 kg, and 0.2 or 0.4 mL per injection to those who weigh > 40 kg. It is expected that one or more of these dose levels will be able to provide adequate LVO and EBD in these groups of pediatric patients with a limited transthoracic echocardiographic window.

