16 CLINICAL PROTOCOL AMENDMENT SUMMARIES

16.1 Amendment A01

16.1.1 Reasons for Amendment

- The requirement for a minimum of 10 subjects to be enrolled in each body weight group is removed.
- The requirement to record the vial code in the CRF is removed.

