2.2 Study Design

This is a Phase 4, open-label, non-randomized, multi-center, multi-dose study in North America and Europe. The study is designed to evaluate overall efficacy and safety of intravenous administration of OPTISON at various doses in pediatric patients undergoing transthoracic echocardiography.

Approximately 50 pediatric patients between ≥ 9 and <18 years of age weighing ≥ 20 kg who are clinically indicated for a transthoracic echocardiogram and are likely to have a limited transthoracic echocardiographic window based on body habitus and/or previous cardiac operation or have a previous suboptimal non-contrast echo cardiogram will be enrolled into the study. Per FDA Advice/information request dated 2023, February 16th, a reduction of the sample size to 30 evaluable subjects was agreed.

OPTISON will be administered according to pediatric body weight (≥ 20 to ≤ 28 kg, >28 to ≤ 40 kg, and >40 kg). Each patient will receive administrations of 2 different dose levels. Up to 3 injections per dose level are allowed to be administered if significant technical issue(s) have occurred e.g., patient related needs, scanner malfunction, or drug injection error, with the total injected dose not to exceed the value defined in Table 1. Injections should be at least 10 minutes apart between the 2 dose levels to allow for clearance of the previous dose.

Table 1 OPTISON Dosing Table

Body weight (kg)	Dose/injection (mL) Dose level 1	Dose/injection (mL) Dose level 2	Total dose (mL) not to exceed (3 injections/dose level)
≥ 20 to ≤ 28	0.1	0.2	1.0
>28 to ≤ 40	0.2	0.3	1.5
>40	0.2	0.4	1.8

[figure not shown]
For echocardiographic imaging, standard apical 4-chamber and 2-chamber views will be obtained at baseline using tissue harmonic imaging, thereafter with contrast using a contrast-imaging mode. Additional views may be obtained at the clinician's discretion. All image views will be obtained prior to and after contrast administration until 10 minutes post injection. All images will be recorded on disk and sent to sponsor's image core lab for preparation of blinded image evaluation (BIE).

Efficacy of echocardiographic images will be evaluated by independent blinded readers based on characteristics of left ventricular opacification (LVO), diagnostic confidence of LV EBD and wall motion, and diagnostic confidence of LVEF. Echocardiographic Analyses as per independent review charter includes:

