2.3 Sample Size

Although this is a dose-finding study and no hypotheses are being tested, it was thought useful to estimate sample size based on one of the study endpoints as a guide. Since there is no historical literature about LV EBD results for OPTISON, the power estimation is based on the endpoint of contrast enhancement duration.

A paired t-test was used for this power analysis with a one-sided significance level of 0.025. The null hypothesis is that the mean value of (contrast enhancement duration for

the high dose – contrast enhancement duration for the low dose within the same patient) ≤ 0 minutes, and the alternative hypothesis is that the mean value of (contrast enhancement duration for the high dose – contrast enhancement duration for the low dose within the same patient) > 0 minutes. Based on the results from [Cohen et al. 1998], we assume that the estimated mean value of (contrast enhancement duration for the high dose – contrast enhancement duration for the low dose within the same patient) equals 0.7 minutes, with a standard deviation of 1.5 minutes. [Table 3](#) displays the power calculation for the hypothesis testing with different sample sizes.

Table 3 Power Calculation

Total sample size	Power
30	70%
40	82%
50	90%
60	94%
70	97%
80	98%

Therefore, the sample size for this clinical investigation was approximately 50 subjects, which would provide at least 90% power to detect an efficacy difference of 0.7 minutes between the high and low doses, with the greater duration for the high dose. In addition, a sample size of 50 was considered to be adequate to address the other efficacy endpoints (LV EBD, LVO characteristics, wall motion assessment, and diagnostic confidence for the evaluation of LVEF) and OPTISON’s safety profile following intravenous administration in pediatric subjects. The data will support dosing information in children. Per FDA Advice/information request dated 2023, February 16th, a reduction of the sample size to 30 evaluable subjects was agreed.

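### The power and dosing statements in SAP 2.3 rest on one pooled contrast; nothing assures usable data in each of the three weight bands that set the dose

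*SAP*

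**What the plan says.** **Power.** SAP 2.3 (repeating Protocol 12.5) states that "A paired t-test was used for this power analysis with a one-sided significance level of 0.025" and that "the power estimation is based on the endpoint of contrast enhancement duration", which is a secondary endpoint. The within-patient difference, high dose minus low dose, is assumed to be such that it "equals 0.7 minutes, with a standard deviation of 1.5 minutes". Table 3 lists power against total sample size: 70% at 30, 82% at 40, 90% at 50. The text then describes a trial of about 50 subjects, "which would provide at least 90% power to detect an efficacy difference of 0.7 minutes between the high and low doses". SAP 2.2 and 2.3 both add that "a reduction of the sample size to 30 evaluable subjects was agreed". Just before that addition in 2.3 stands the sentence "The data will support dosing information in children".

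**Dose.** SAP Table 1 sets dose level 1 and dose level 2 per injection by body weight: 0.1 and 0.2 mL at 20–28 kg, 0.2 and 0.3 mL at >28–40 kg, 0.2 and 0.4 mL at >40 kg.

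**Numbers per band.** Entry is at age 9 to under 18 years and at least 20 kg. Protocol 6.1 sets no number per band, and 16.1.1 explains why: "The requirement for a minimum of 10 subjects to be enrolled in each body weight group is removed". Protocol 6.2.1 says of US boys and girls that "children > 9 years of age usually weigh > 28 kg and children > 12 years of age usually weigh > 40 kg", and goes on to say that weight differs widely at any given age.

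**Reporting.** SAP 6.4.2 and 6.4.3 summarise efficacy overall and for two groups, ≤40 and >40 kg. The subject-level suitability composite is tabulated by dose level. The three dosing bands appear only as a baseline characteristic in SAP 6.1.1.

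**The concern.** The primary objective is to determine a suitable dosage, and the dosage under test depends on weight band. The only quantitative support for the sample size does not. There is no single high dose or low dose: 0.2 mL is the higher level in the lightest band and the lower level in the other two. The pooled contrast averages dose steps of 0.1, 0.1 and 0.2 mL and assumes a common effect of 0.7 minutes.

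As written, a favourable overall or ≤40 kg result could be taken as evidence for the 20–28 kg band even if few children in that band contributed. The ≤40 kg row is not a substitute, because its dose level 1 mixes 0.1 and 0.2 mL and its dose level 2 mixes 0.2 and 0.3 mL. At stake is a dosing statement for the lightest children that rests mainly on heavier children given other volumes.

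**Working it through.** **1. Reproduce Table 3.** Inputs from SAP 2.3: mean difference 0.7 min, SD 1.5 min, paired t-test, one-sided alpha 0.025. Power is the probability that a noncentral t variable with n − 1 degrees of freedom and noncentrality (0.7/1.5)·√n exceeds the 97.5% point of the central t.

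| Total n | Stated | Recomputed |
|---|---|---|
| 30 | 70% | 69.5% |
| 40 | 82% | 82.1% |
| 50 | 90% | 89.9% |
| 60 | 94% | 94.5% |
| 70 | 97% | 97.1% |
| 80 | 98% | 98.5% |

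For n = 30 the noncentrality is 0.467 × 5.477 = 2.56. The table is sound for what it describes, one contrast on all subjects. (Strictly, reaching 90% needs 51; this is rounding.)

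**2. Apply the same inputs within one band.** The 0.7 min effect is kept only for comparison; the documents give no effect by band.

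| n in band | Power | 95% CI half-width for mean difference |
|---|---|---|
| 3 | 7% | 3.7 min |
| 5 | 13% | 1.9 min |
| 8 | 21% | 1.2 min |
| 10 | 26% | 1.1 min |
| 20 | 51% | 0.7 min |

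The half-width is t(0.975, n − 1) × 1.5/√n; for n = 10 it is 2.262 × 1.5/3.162 = 1.07. An equal split of 30 is 10 per band, hence 26%. About 31 children in one band would be needed for 70%, 39 for 80% and 51 for 90%.

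**3. How many children might fall in the 20–28 kg band?** The documents give no share, so it is assumed over a range. Expected count = 30 × share; the probabilities are binomial.

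| Assumed share | Expected of 30 | P(none) | P(at least 10) |
|---|---|---|---|
| 2% | 0.6 | 55% | <0.1% |
| 5% | 1.5 | 22% | <0.1% |
| 10% | 3.0 | 4% | <0.1% |
| 20% | 6.0 | 0.1% | 6% |

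The growth statement and the entry age point towards the low-to-middle part of this range but do not fix it.

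**4. Precision of the suitability composite.** If a dose met the composite in every one of n children, the exact (Clopper–Pearson) 95% lower limit is 0.025^(1/n):

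- n = 3: 29%
- n = 5: 48%
- n = 10: 69%

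These are best cases; any child not meeting the composite lowers the limit.

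**The case against.** The best defence is that the study is descriptive. Both documents say no hypotheses are tested and call the power calculation a guide. Suitability is a subject-level composite, weighed with image quality, diagnostic confidence and safety (Protocol 10.2.1). The objective as worded asks for a suitable dosage in pediatric patients, not one per band. The within-patient contrast of level 2 against level 1 is coherent as a pooled quantity. Table 3 is headed by total sample size and prints the 70%. The 90% and adequacy sentences are in the past tense and refer to 50. Band counts will be visible at baseline, and the SAP says the reduction to 30 was agreed following FDA advice.

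Much of this stands. It removes any claim that the sample size is wrong or that each band had to be powered. It does not cover the dosing sentence, which has no limit by band. Nor does either document report any agreement about numbers per band. A descriptive study still has to show the precision of what it describes.

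Three stronger readings are tempting and should be resisted:

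- *The 20–28 kg band will be nearly empty.* The growth statement says what is usual among US children, is qualified at once, and gives no proportion. The trial enrols echocardiography patients in North America and Europe. A small band is a fair inference; a near-zero count is an assumption.
- *No dosing conclusion could be drawn for that band.* This depends on the count achieved. Low power for a duration test makes a descriptive statement imprecise; it does not forbid one.
- *The former minimum of 10 should become a cut-off for conclusions.* It was an enrolment requirement, deliberately removed. Power is 21% at 8 and 26% at 10, so nothing changes sharply there.

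**Conclusion.** The point holds as a gap in reporting and precision. The 90% and 70% figures are correct for a single pooled contrast in enhancement duration and apply to none of the three dose pairs. Nothing in the current documents assures a usable number in every band, and the general dosing sentence does not acknowledge this.

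The 26% at 10 per band assumes an equal split and the plan's own effect and SD. The 0.6 to 6 children expected in the lightest band rests on assumed shares of 2% to 20%. The lower limits of 29%, 48% and 69% need no assumption about effect size, only the count and uniform success. The documents do not support a prediction of the band's actual size or a blanket bar on concluding anything about it.

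**What to change.** 1. In SAP 2.3, state that with 30 evaluable subjects the power is about 70%, for the pooled high-minus-low contrast in enhancement duration only, and for no single weight band.
2. Qualify the dosing sentence: any dosing statement for a weight band rests on that band's own data and precision, not on the overall or ≤40 kg result.
3. Add to SAP 6.4.3 and the table list one table giving n and an exact 95% CI for the dose-suitability composite, for each of the three dosing bands at each dose level, by reader. That is 3 × 2 × 3 = 18 estimates per analysis population.

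The cost is a few sentences and one small table, with no extra enrolment or data collection. The downside is wide intervals, which may show openly that the lowest band is not informative.

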2.4 Interim Analysis

There is no interim analysis planned for this study.

2.5 Randomization and Blinding

This is an open-label study. No blinding will be conducted for the subject allocation or application of the investigational medicinal product (IMP) in this study.

For determination of efficacy and optimal dose level, 3 qualified independent blinded readers will conduct BIE of echocardiographic images. Non-contrast and OPTISON-

enhanced images will be presented in random order to the 3 readers without dosing information.

3 STUDY ENDPOINTS

3.1 Primary Endpoint

- Visualization of the 12 segments of the left ventricle wall in standard apical 4-chamber and 2-chamber views measured by the qualitative EBD visualization scale.

3.2 Secondary Endpoints

The secondary endpoints will be the following:

- Overall safety profile in terms of occurrence of AEs and changes in vital signs, arterial oxygen saturation (SaO₂), physical examinations, and 12-lead ECGs following administration of different OPTISON doses in pediatric patients.
- LVO assessed by visual peak contrast intensity and peak LV contrast filling, and duration of contrast enhancement following intravenous administration of OPTISON at various doses.
- Comparison of diagnostic confidence of LV EBD and wall motion between non-contrast and OPTISON-enhanced echocardiography at various doses.
- Comparison of diagnostic confidence in the evaluation of LVEF between non-contrast and OPTISON-enhanced echocardiography.

4 ANALYSIS POPULATIONS

4.1 Definition for Analysis Populations

Enrolled subjects are subjects who signed the informed consent.

4.1.1 Safety Population

The Safety Population will include all subjects enrolled in the study who receive ≥ 1 administration of OPTISON.

4.1.2 Full Analysis Set (FAS) Population

The FAS population will include all subjects enrolled in the study who have available non-contrast harmonic images and OPTISON-enhanced echocardiographic images, irrespective of the quality of CE-ECHO.

4.1.3 Per-Protocol (PP) Population

The PP population will include all subjects in the FAS population who do not have important protocol deviation impacting the study primary endpoint.

5 ANALYSIS CONVENTIONS

Post-text tables and listings will be prepared in accordance with the current International Council for Harmonisation (ICH) Guidelines. The information and explanatory notes to be provided in the “footer” or bottom of each table and listing will include the following information:

1. Date and time of output generation
2. SAS® program name, including the path that generates the output
3. Any other output specific details that require further elaboration

In general, tables will be formatted with a column displaying findings recorded on the electronic case report form (eCRF) for all subjects combined. Row entries in tables are

made only if data exists for at least one subject (*i.e.*, a row with all zeros will not appear). The only exception to this rule applies to tables that list the termination status of subjects (*e.g.*, reasons for not completing the study). In this case, zeros will appear for study termination reasons that no subject satisfied. The summary tables clearly indicate the number of subjects to which the data apply and unknown or not performed are distinguished from missing data.

Supportive individual Subject Data Listings, as a minimum, will be sorted and presented by weight group, subject number, visit date, and dose level if applicable. Listings will also include days relative to the first dose of study drug, if applicable.

Specific algorithms are discussed for imputing missing or partially missing dates, if deemed appropriate, under specific data topics. Imputed or derived data are flagged in the individual subject data listings. Imputed data are not incorporated into any raw or primary datasets. These data are retained in derived (or analysis) datasets.

This section details general conventions to be used for the statistical analyses. The following conventions will be applied to all data presentations and analyses.

- Summary statistics for categorical variables will consist of the number and percentage of responses in each level. The number and percentage of responses will be presented in the form XX (XX.X%).
- Summary statistics for continuous variables will consist of the sample size (n), mean, standard deviation (SD), median (1st and 3rd quartile), minimum, and maximum values.
- All mean and median values, as well as Q1 and Q3, will be formatted to one more decimal place than the measured value. Standard deviation values will be formatted to two more decimal places than the measured value. Minimum and maximum values will be presented with the same number of decimal places as the measured value.
- All p-values, if applicable, will be rounded to 4 decimal places. All p-values that round to 0.0000 will be presented as ‘<0.0001’ and p-values that round to 1.0000 will be presented as ‘>0.9999’. Two-sided P-values < 0.05 will be considered to be statistically significant unless otherwise specified.
- All summary tables will include the analysis population sample size (*i.e.*, number of subjects).

- Study Day 1 is defined as the date at which the subject receives the first dose of study medication. All study days are determined relative to Day 1.
- Study days prior to Day 1 will be calculated as:
 - Study Day = Assessment Date – First Injection Date
- Study days after Day 1 will be calculated as:
 - Study Day = Assessment Date – First Injection Date + 1.
- Baseline values will be defined as the last non-missing value recorded prior to first dose of study drug.
- Change from baseline will be calculated as follows: Change = Post-baseline value - baseline value.
- All pre- and post- investigational product assessments including unscheduled or repeat assessments will be included in the data listings. For unscheduled or repeat pre-dose assessments, the last assessment taken for a time point will be used in the data summaries (summary tables, figures, and statistical analysis); for all post-dose time points, the initial assessment for any given time point will be used in the safety data summaries (summary tables, figures, and statistical analysis, except the summary tables of clinically notable values and shift tables where all values will be included). For efficacy summaries, the site records in the eCRF which assessment was considered for the image interpretation. The corresponding assessment will be used in the efficacy summaries.
- Date variables will be formatted as DDMMYY for presentation.
- Tables, figures, and listings will be presented in landscape orientation.
- SAS® Version 9.4 or higher will be the statistical software package used for all data analyses.

Definition of Analysis Windows

There are no visit windows for this study. For the statistical analyses, data will be analyzed by the nominal visit that was collected on the electronic case report form (eCRF).

Unscheduled visits will not be used in the by-visit analysis, but will be used for the following where appropriate: 1) derivations of baseline/last on-treatment measurements; 2) derivations of the maximum/minimum on-treatment values and maximum/minimum changes from baseline values for safety analyses; 3) data listings.

Definition of Missing Data Imputation

Missing values will not be substituted by estimated values but treated as missing in the statistical evaluation. Data for all enrolled participants will be presented in the data listings. A participant who is enrolled but who did not receive any amount of study drug will be included in those data listings for which they have data but will be excluded from all data summaries.

Missing or partial dates for AE or for medications may be imputed for determination of treatment emergent AE (TEAE) or concomitant medication, as follows.

- If the AE start date is completely missing, then the AE will be considered treatment emergent unless it can be determined that the AE end date/time occurred prior to IMP injection. If this is the case, the AE will not be considered treatment emergent.
- If the AE start date/time is partially missing and the partial date is not sufficient to determine if the event occurred after the IMP injection, then the AE will be considered treatment emergent unless it can be determined that the AE end date/time occurred prior to the injection.

6 STATISTICAL ANALYSES

6.1 Demographics, Baseline Characteristics, Medical History, and Prior/Concomitant Medications

6.1.1 Demographic and Baseline Characteristics

Age (years between birth and time informed consent form was signed), sex, race, ethnicity, and baseline height, weight, weight group (≥ 20 to ≤ 28 , > 28 to ≤ 40 , > 40 kg; as well as ≤ 40 , > 40 kg), and body mass index (BMI) will be summarized overall, independent of IMP assignment, based on Safety, FAS, and PP populations.

Categorical data (sex, weight group, race, and ethnicity) will be summarized using frequencies and percentages. The number of subjects with missing information will also be summarized.

Continuous data (age, baseline height, weight and BMI) will be summarized with the number of non-missing observations by mean, standard deviation, median, Q1, Q3, minimum and maximum values.

